## **9 STATISTICAL CONSIDERATIONS**

### **9.1 General Design Issues**

Our hypothesis is that for each medication class, the intervention will produce clinically relevant decreases in mean possession rates of 10% of a standard deviation in patients seen in intervention clinics compared to those who are seen in control group clinics.

The study design was chosen to meet the requirements of the funder for a non-pharmacologic/non-device intervention for people living with dementia, conducted in a health system setting. The 24-months of funding is for a demonstration project, intended to demonstrate the feasibility and acceptability of the intervention, but with the stipulation by the funder that the trial must be a randomized controlled trial, one with a control group. In response, we proposed a cluster-randomized trial where the intervention will be randomized at the primary care clinic level, not the patient level, and existing health systems claims data will be used to address our primary outcome (Specific Aim #1) and one of our secondary outcomes: Specific Aim #2: emergency department visits and hospitalizations for a fall.

The primary outcome measure for this study will be medication possession rates (MPR) per quarter, for the 3 therapeutic classes of medications - antipsychotics, benzodiazepines, and hypoglycemics - that are considered low-value for beneficiaries with dementia. Unlike many studies using medication possession rates to exam adherence, we are interested in reducing, not increasing, the percent of days covered. Following an intent-to-treat design, claims data from all Medicare beneficiaries meeting our dementia eligibility criteria prior to the start of the value champion intervention will be included in the analysis. To determine the impact of the intervention, we will construct hierarchical models with time period observations nested within patient. These models will be random effects or generalized estimating equations (GEE) with robust standard errors, and will be either linear, if original MPRs are used as outcome, or generalized linear, if transformation necessary. The key variable of interest in these models will be the treatment indicator (assigned based on practice randomization to intervention or control group).

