### **9.2 Sample Size and Randomization**

Our sampling plan anticipates enrolling at least 30 of the 39 practices in USMM and 26 of the 28 practices in Ochsner. Based on Medicare enrollments of 39,000 members in USMM with a 20 percent dementia rate in 2019, and 10,000 members in Ochsner with approximately 10 percent of members diagnosed with dementia in 2019, we should have

at least 2,000 patients per treatment group for USMM and 500 patients per treatment group for Ochsner. For our primary outcome, with a follow-up period of one year and with mediation possession rates calculated per patient each quarter, we will have approximately 4 MPR observations per patient or 8,000 observations per group for USMM analyses and 2,000 per group for Ochsner. Even after assuming significant correlation across time within patient and modest correlation between patients within a practice, which will reduce effective sample sizes by 20%, we should have the equivalent of 6,400 observations per treatment group for our USMM analyses and 1,600 observations per treatment group for Ochsner.

The expectation of our intervention is that for each medication class, it will produce clinically relevant decreases in mean possession rates of 10% of a standard deviation. If the effect size is this large for a medication class and using a 5% level of significance, our Ochsner sample (with effective size of at least 1,600 per group) will have 80% power to discern a significant difference, while our larger USMM sample (with effective size of at least 6,400 per group) will have almost 100% power. Indeed, our USMM sample will have 80% power to find a significant difference, even if the effect size is only 5% of a standard deviation

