### 9.4 Outcomes

#### 9.4.1 Primary outcome

The primary outcome for this study (Specific Aim #1) will be medication possession rates (MPR) per quarter, for the 3 therapeutic classes of medications - antipsychotics, benzodiazepines, and hypoglycemics - that are considered low-value for beneficiaries with dementia. These beneficiary-level measures are calculated as quotients with denominator equal to the length of the quarter and the numerators equal to the days supply for prescriptions within the class filled during the quarter, plus excess days-supply from the previous period minus excess days-supply remaining at the end. Unlike many studies using medication possession rates to exam adherence, we are interested in reducing, not increasing, the percent of days covered. As a first choice, we will try to use originally-valued MPR variables in regression modeling, but if they don't reflect adequate

fit, we will transform them or possibly convert them to ordinal variables instead. For example, Benner and colleagues in their study of statin adherence defined non-adherence as MPRs within 0-20 percent, low-adherent as between 21-79 percent and high adherence as 80 percent or higher. In addition to MPRs, we will also calculate and analyze the number of 30-day prescriptions per time-period for each beneficiary in the study.

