### 9.5 Data Analyses

Following an intent-to-treat design, all Medicare beneficiaries meeting our dementia eligibility criteria will be included in the study, regardless of level of engagement with practice clinicians. Data analysis will begin with descriptive statistics, comparing the mix of patients at each practice including demographics, chronic conditions, and incident versus prevalent dementia. This will allow us to check for balance between treatment and control practices and inform subsequent modeling. To determine the impact of the intervention, we will construct hierarchical models with time period observations nested within patient. These models will be random effects or generalized estimating equations (GEE) with robust standard errors, and will be either linear, if original MPRs are used as outcome, or generalized linear, if transformation necessary. The key variable of interest in these models will be the treatment indicator (assigned based on practice). Since there could well be a time effect of treatment, we will explore several model specifications, such as discrete indicators for the time periods or a single continuous variable. Interactions of treatment with time period will also be explored. By examining various different specifications involving time, we should be able to determine whether the intervention leads to a one-time change, a gradual trend over time, or a combination of both (an immediate jump with a further change, as time passes). Finally, we will explore the impact of this intervention on health inequities by stratifying our primary analysis by race/ethnicity.

Specific to Aim #3: Current approaches to evaluating implementation outcomes are still nascent, with few measures that have validated psychometric properties. Conceptually, these measures are inter-dependent, and are connected with service outcomes, such as patient safety. We will use data collected from interviews with the Value Champions to conduct a thematic analysis of the five implementation outcomes using a deductive approach.

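### No single primary contrast is fixed, so a fit-driven change of outcome scale or reliance on a time slope could leave the powered 0.10 SD difference in mean MPR untested

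*Combined protocol and SAP*

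**What the plan says.** All references are to the combined protocol and SAP.

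- **Hypothesis and power.** Sections 1.1 and 9.1 state the hypothesis for each medication class, and Section 9.2 powers it: "clinically relevant decreases in mean possession rates of 10% of a standard deviation", "using a 5% level of significance". Power is given separately by ACO: "our Ochsner sample (with effective size of at least 1,600 per group) will have 80% power to discern a significant difference" and "our larger USMM sample (with effective size of at least 6,400 per group) will have almost 100% power".
- **Outcome scale.** Section 9.4.1 prefers MPR on its own scale. If fit is not adequate, "we will transform them or possibly convert them to ordinal variables instead". It gives no fit criterion, no named transformation and no binding cut-points; the three bands from a statin study are only an example.
- **Model class.** Section 9.1, repeated in 9.5: "These models will be random effects or generalized estimating equations (GEE) with robust standard errors". The model is linear or generalized linear according to the scale.
- **Time.** Section 9.5: "we will explore several model specifications, such as discrete indicators for the time periods or a single continuous variable", and then "Interactions of treatment with time period will also be explored". The purpose given is to tell a step change from a trend or a mixture of the two.
- **What is named.** Sections 9.1 and 9.5 make the treatment indicator the variable of main interest. Section 9.5 also refers to a primary analysis, to be stratified by race/ethnicity, without saying which of these models it is. Comparisons of treatment and control practices are to inform the modelling, so the model choice is not described as blind to arm.

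**The concern.** The hypothesis and the power calculation concern one quantity: the difference between arms in mean MPR, in SD units. The analysis sections permit models that estimate something else, and they do not say which estimate decides the primary question. If the scale is changed after the fit is inspected, or if the conclusion rests on a trend or interaction term, the trial reports a test of a hypothesis that was neither stated nor powered. This would be so even if every choice were made in good faith. There is also a question about the 5% level, because several contrasts will be fitted and none is designated in advance.

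**Working it through.** **1. Reproduce the stated power.** Inputs from Section 9.2: effective sizes 1,600 and 6,400 per group, effects 0.10 and 0.05 SD, 5% level. Sidedness is not stated. The effective sizes are taken as given; whether the 20% allowance for correlation is enough is a separate matter.

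Power = Φ(d / √(2/n) − 1.96).

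- n = 1,600, d = 0.10: 0.10/0.03536 = 2.828, and Φ(0.868) = 80.7% (stated 80%).
- n = 6,400, d = 0.10: 0.10/0.01768 = 5.657, and Φ(3.697) = 99.99% (stated almost 100%).
- n = 6,400, d = 0.05: Φ(0.868) = 80.7% (stated 80%).

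A one-sided 5% test would give 88.2% in the first and third cases, so the calculation is two-sided. The figures reproduce, and they apply to a difference in means.

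**2. What each time specification tests.** Take two effect patterns over four quarters, as reductions in SD units, each with mean 0.10:

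- Constant: 0.10, 0.10, 0.10, 0.10. Mean = 0.40/4 = 0.10.
- Gradual: 0.04, 0.08, 0.12, 0.16. Mean = 0.40/4 = 0.10.

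The treatment-by-linear-time slope is Σ w·d / 5 with weights w = −1.5, −0.5, 0.5, 1.5.

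- Constant: 0.10 × (−1.5 − 0.5 + 0.5 + 1.5)/5 = 0.
- Gradual: (−0.06 − 0.04 + 0.06 + 0.24)/5 = 0.04 per quarter.

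Under the constant pattern the powered effect is fully present, yet a slope test rejects only at its 5% false-positive rate. Naming the treatment indicator as the key variable does not settle this. Once treatment-by-quarter terms enter with quarter 1 as reference, its coefficient is the quarter-1 effect: 0.10 under the constant pattern and 0.04 under the gradual one, not the average.

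Without interactions and with balanced quarters, time is orthogonal to treatment, so indicators and a continuous term give the same treatment coefficient. In one simulated trial it was −0.00306 with p = 0.625 under both forms. The interactions matter; the main-effect form of time hardly does.

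**3. What a change of scale tests.** With the example bands in Section 9.4.1 (0–20, 21–79, 80 or more), a patient who goes from 79% to 21% of days covered drops 58 points in MPR and does not change category. A transformed outcome likewise gives a difference on the transformed scale. Neither is the 0.10 SD mean difference. Random effects and GEE target the same mean difference while the model is linear, so that choice affects the target only after a switch to a generalized linear model.

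**4. False-positive rate.** Null simulations of 4,000 trials each; the standard error near 5% is √(0.05 × 0.95/4,000) = 0.34 points.

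- *Scale chosen on fit.* Assumed: 58 clinics, 86 patients each, 16% users, between-clinic correlation 0.02 on a latent scale. Choosing the scale with lowest skewness, ignoring arm, rejected in 5.7%, against 5.7–5.8% for the single-scale tests in the same run. Taking the smallest p-value across scales gave 7.4%.
- *Any significant contrast reported.* 500 patients per arm and four quarters (Section 9.2, Ochsner). Assumed: 20% users, beta-distributed MPR among users, no practice clustering, latent quarter-to-quarter correlation 0.7 / 0.9 / 0.97. The average-level test alone rejected in 5.6% / 5.0% / 4.6%. At least one p < 0.05 occurred as follows:
  - level and trend: 10.2% / 9.5% / 9.4%
  - adding last quarter and a 4-df test by quarter: 14.3% / 13.3% / 13.0%
  - adding ordinal level and trend: 15.9% / 15.1% / 15.0%
- *Same question with clinic clustering.* Assumed: 58 clinics of 86, 16% users, ICC 0.02, clinic-level tests. Single tests gave 4.9–5.4%, the best of three time forms 11.0%, and the best of seven combinations 14.0%.

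**The case against.** The best defence is that the plan is more disciplined than it first looks. Untransformed MPR is the declared preference, and the scale changes on fit, not on significance. The treatment indicator is the named variable of interest. Section 9.1 states the analysis with no search over time at all. Section 9.5 uses the language of exploration for the interactions, which describe the shape of an effect. The study is also a demonstration project on feasibility and acceptability.

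Much of this stands. A reader might infer that following the plan as written means the primary p-value is no longer a 5% test. The documents do not support that: a scale chosen on fit and blind to arm left the rejection rate unchanged in step 4, and no section says that the most significant time form will be reported. A reader might also infer that the linear model is bound to fail because most patients take none of a given class. Section 2.1 cites 14.3% for antipsychotics and up to 20% for benzodiazepines, but also 35.2%, 24.2% and 16.3% for hypoglycemic regimens in elderly patients with A1c below 7%. No fit criterion is given, so a switch is a realistic prospect and not a certainty.

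What the defence does not answer is the target of the test. The plan never labels the time work exploratory relative to a fixed primary contrast, and a blind, fit-based switch still moves the analysis off the powered mean difference.

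**Conclusion.** The point holds as a mismatch between the hypothesis that is stated and powered and the analysis that may be run. A switch to a transformed or ordinal outcome, or a conclusion resting on a slope, would leave the 0.10 SD difference in mean MPR untested. In the clearest case, an immediate and constant drop, the slope is exactly zero and the slope test has 5% rejection, against the 80.7% computed for the mean difference. This follows from the text and from algebra and needs no simulation.

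The effect on the error rate is secondary. The range of roughly 9–16% per class assumes that any significant time contrast could be reported as the primary result, and it rests on assumed user proportions and correlations. It is an illustrative worst case, not a property of the stated rule. Nor should it be compounded across classes: 1 − (1 − 0.14)³ = 36% treats the three classes as independent and brings in multiplicity across classes, which is a separate question.

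**What to change.** Before outcome data are analysed by arm, name one primary contrast per medication class for each analysis that Section 9.2 powers (USMM and Ochsner): the treatment effect on untransformed quarterly MPR, averaged over the four quarters. Estimate it from a linear model with quarter indicators and the age and sex covariates already planned in Section 9.4.2, with standard errors clustered on practice and a small-sample correction. Keep this contrast whatever the residual fit; with robust errors, the linear model remains valid for a mean difference despite many zeros. Label the transformed, ordinal, trend and treatment-by-time models as secondary or exploratory.

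The cost is a few sentences in Sections 9.4.1 and 9.5. The downside is that the primary scale can no longer be changed; every other model can still be fitted and reported. The documents do not show whether outcome data have already been examined, so the amendment should state that.

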### Objectives

The primary objective is to assess the effectiveness of training a clinician to be a 'value champion' within their clinical setting to decrease the use of three classes of potentially inappropriate prescription medications (PIMs) among people living with dementia.

(PLWD) Secondary objectives include determining if the intervention is associated with a reduction in emergency department (ED) visits or hospitalizations due to a fall, and examining five implementation outcomes: appropriateness, feasibility, fidelity, penetration, and equity.

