#### 9.4.2 Secondary outcomes

As a secondary outcome, for Specific Aim #2, we will also assess the incidence of falls during the study window. Falls are difficult to monitor using claims data, but Min and colleagues have developed a method that IAC and Brandeis staff (Co-Investigator [name]) have helped test for ICD-10. We will use the most conservative definition that looks for the presence of fall ‘reason for visit’ code on ED, ambulatory, or inpatient visit as indicated by a clinician bill (Part B). Key covariates in all of our regression models will include age and sex, both derived from the Medicare beneficiary summary files, house at IAC.

For Specific Aim #3, the five important implementation outcomes: appropriateness, fidelity, feasibility, and penetration will be assessed by analyzing interviews with clinician value champions. The Clinician interviews will provide us with data we need to assess the implementation outcomes.

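### The exploratory health-inequity analysis in section 9.5 stratifies by race/ethnicity but does not, as written, estimate or test whether the effect differs between groups

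*Combined protocol and SAP*

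**What the plan says.** The last sentence on the claims analysis in section 9.5 (Data Analyses) reads: "we will explore the impact of this intervention on health inequities by stratifying our primary analysis by race/ethnicity". The documents say no more about this analysis. They do not define the race/ethnicity categories or give their sizes, and they state neither how the stratum results will be compared nor how they will be interpreted.

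The same paragraph does plan interactions for another purpose: "Interactions of treatment with time period will also be explored". On covariates, section 9.4.2 says "Key covariates in all of our regression models will include age and sex"; race/ethnicity is not named there.

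Equity also appears elsewhere, in a different role. The Précis (Objectives) speaks of "examining five implementation outcomes: appropriateness, feasibility, fidelity, penetration, and equity". Section 9.5 assigns these to the value-champion interviews, which will be used to "conduct a thematic analysis of the five implementation outcomes using a deductive approach".

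Section 9.2 gives power for each whole ACO sample and none for subgroups.

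**The concern.** The stated aim is comparative: does the intervention change differences between groups? The quantity that answers it is the treatment effect in one group minus the treatment effect in another, with its uncertainty. Repeating the primary analysis in each stratum gives the two effects separately and leaves the comparison to the reader.

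The usual shortcut is to note which strata reach significance. That mixes the size of the effect with the amount of information in each stratum. A smaller group can miss significance with exactly the same true effect, and the result may then be reported as the intervention having failed that group. This is the only quantitative, patient-level analysis of inequity that the documents describe, so it may well be quoted.

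**Working it through.** **Inputs from the plan.** Section 9.2 gives the level ("using a 5% level of significance", sidedness not stated), the effect ("it will produce clinically relevant decreases in mean possession rates of 10% of a standard deviation") and the power ("our Ochsner sample (with effective size of at least 1,600 per group) will have 80% power to discern a significant difference"). For USMM it gives 6,400 effective observations per group, with nearly 100% power at 0.10 SD and 80% at 0.05 SD. Allocation is 1:1 (section 4.3). Pooling the ACOs gives 6,400 + 1,600 = 8,000 per group. Each calculation applies to one medication class.

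**Assumptions.** There are two race/ethnicity groups, the smaller holding a share s of 10, 20, 30 or 50% of the effective sample. The documents give no shares. The strata are treated as independent.

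**Step 1: reproduce the plan's power.** In SD units, SE = √(2/n) and power = Φ(d/SE − 1.96).
- Ochsner, d = 0.10: SE = √(2/1,600) = 0.0354; Φ(2.828 − 1.96) = 80.7%. A one-sided test would give 88.2%, so the stated 80% implies a two-sided test.
- USMM: 99.99% at d = 0.10 and 80.7% at d = 0.05.

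The plan's figures reproduce.

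**Step 2: same true effect in both strata.** Let p1 and p2 be the power with n·s and n·(1 − s) per arm. Then P(exactly one significant) = p1(1 − p2) + p2(1 − p1).

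Ochsner at s = 20% has 320 and 1,280 per arm, so p1 = 0.244 and p2 = 0.716. The probability is 0.244 × 0.284 + 0.716 × 0.756 = 0.069 + 0.541 = 0.61. The second term, 54%, is the case where only the larger group is significant.

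| Smaller share | Ochsner: power in smaller stratum | Ochsner: exactly one significant | USMM: power in smaller stratum | USMM: exactly one significant | Pooled: exactly one significant |
|---|---|---|---|---|---|
| 10% | 14% | 69% | 43% | 57% | 48% |
| 20% | 24% | 61% | 72% | 28% | 19% |
| 30% | 34% | 55% | 87% | 13% | 7% |
| 50% | 52% | 50% | 98% | 4% | 1% |

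All rows use d = 0.10. At d = 0.05, USMM gives the Ochsner discordance column (69/61/55/50%), because d/SE is then the same.

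**Step 3: the interaction.** SE of the difference = √(2/(ns) + 2/(n(1 − s))). If the true effects are equal, a 5% interaction test declares a difference 5% of the time. If the effect is 0.10 SD in one group and zero in the other, with s = 20%:
- Ochsner: SE = √(0.00625 + 0.00156) = 0.0884; power = Φ(1.131 − 1.96) = 20%; 95% CI half-width 1.96 × 0.0884 = 0.17 SD.
- USMM: SE = √(0.00156 + 0.00039) = 0.0442; power = Φ(2.263 − 1.96) = 62%; half-width 1.96 × 0.0442 = 0.09 SD.

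For shares of 10/20/30/50%, power is 13/20/25/29% at Ochsner and 40/62/74/81% at USMM.

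**Sensitivity to the effective sample size.** The plan's 20% reduction is taken as given; no correlation values are stated. As an assumed example, take within-patient correlation 0.5 and clinic ICC 0.01, with 13 and 16 clinics per arm (half of 26 and of 32). The variance of an arm mean is ((1 + 3 × 0.5)/4 − 0.01)/patients + 0.01/clinics.
- Ochsner: 0.615/500 + 0.01/13 = 0.0020, an effective n of about 500.
- USMM: 0.615/2,000 + 0.01/16 = 0.00093, about 1,070.

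Power within strata would then be lower than in the table.

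**The case against.** The best defence is that the analysis is worded as exploratory, in a demonstration project, and that stratified estimates are a legitimate descriptive display. That is fair, and it limits how much weight the point carries. It does not supply the missing comparison: the exploratory label weakens the claim that may be made, but the question asked still concerns a difference.

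Several stronger readings are tempting and not supported.
- *A reader might infer that the equity implementation outcome is to be judged this way.* It is not. That outcome comes from thematic analysis of interviews, and its standing among the five does not transfer to this claims analysis.
- *A reader might infer that the plan will compare strata informally or by p-value.* The plan states no comparison method. The gap is silence, so the discordance figures are conditional on that reading being made.
- *A reader might infer that stratified results cannot be tested against each other.* They can, with a formal contrast that allows for clinics contributing patients to several strata. The plan does not say this will be done.
- *A reader might take 61% as the general risk.* It is the Ochsner figure at 0.10 SD and a 20% share; the same share gives 28% at USMM and 19% pooled.
- *A reader might blame unequal group sizes alone.* At Ochsner, two equal halves still disagree 50% of the time, because each has only 52% power.

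It can also be objected that an interaction test is weak here. This stands, and it is why the interval for the difference should carry the interpretation.

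**Conclusion.** The point holds as a limited improvement to a stated exploratory method. Section 9.5 sets a comparative aim and names a procedure that does not, as written, estimate or test the comparison, although the same paragraph uses interactions for time. The primary analysis is unaffected.

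The risk of a misleading pattern under equal true effects of 0.10 SD runs from about 1% to 69%, depending on the ACO and on group shares the documents do not give. It is high at Ochsner for every share examined. At USMM it is high only when the smaller group is small or the true effect is nearer 0.05 SD.

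These figures rest on two groups, independent strata and the plan's own effective sample sizes. Clinics shared between strata would tend to correlate the estimates positively, which lowers discordance. Stronger within-patient correlation than the plan allows would lower power in the strata and for the interaction.

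**What to change.** In section 9.5, replace stratification as the sole method with one model fitted across race/ethnicity groups. It should contain treatment, race/ethnicity and their interaction, with standard errors clustered on clinic. Define the categories in advance and say whether the model is fitted within each ACO or across both. Report the group-specific effects and their difference with 95% confidence intervals, treat the stratum results as descriptive, and keep the exploratory label.

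Add a sentence saying that a non-significant interaction will not be read as absence of inequity, and that interpretation rests on the confidence interval for the difference.

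The cost is a few model terms and a few sentences, with no new data beyond the race/ethnicity variable that the stratified analysis already needs. The small downside is the limited power shown above, which the added sentence addresses.
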